4.1. Overview of Study Design

Study I4T-MC-JVDF is an open-label, multicenter Phase 1 study to evaluate the safety and preliminary efficacy of ramucirumab in combination with pembrolizumab. Phase 1a (dose-limiting toxicity [DLT] observation) and Phase 1b (expansion; safety and preliminary efficacy) will include patients with locally advanced and unresectable or metastatic gastric or gastroesophageal junction (GEJ) adenocarcinoma (gastric-GEJ cancer), NSCLC, transitional cell carcinoma of the urothelium (urothelial cancer), or biliary tract cancer (BTC).

Based on the results of Phase 1, the Sponsor will consider various approaches toward developing the combination therapy, including but not limited to an adaptive Phase 2/3 trial design, enrolling additional patients, and/or testing alternative dosing levels and schedules. If sufficient tolerability and activity are demonstrated in Phase 1, the protocol will be amended and resubmitted accordingly.

Figure JVDF.1 illustrates the study design.

Abbreviations: BTC = biliary tract cancer; GEJ = gastroesophageal; L = line; n = number of patients; NSCLC = non-small cell lung cancer; PK = pharmacokinetics; Ram = ramucirumab.

Note: The results of the Phase 1a interim analysis will confirm the dosing regimens to be used in Phase 1b. Dose reductions (ramucirumab), delays, and discontinuations may occur per the guidelines in Section 6.6.

Figure JVDF.1. Illustration of study design.

4.1.1. Phase 1a: Dose-Limiting Toxicity Observation

The DLT observation period of Phase 1a will employ a 3+3 design, enrolling up to 6 patients per dose schedule. Patients will be allocated into one of 2 dose schedules, based on their diagnosis at baseline, as shown in [Figure JVDF.1](#).

The DLT observation period will last for one 21-day treatment cycle (see Section 6.1.1 for selection and timing of doses).

The definition for DLTs and the criteria used to determine progress of the study are provided in Section 6.1.1.1.

4.1.2. Phase 1b: Expansion

If results yield an acceptable number of DLTs (≤ 1) in the observation period of Phase 1a, then the Expansion Phase 1b (Expansion Portion) will start.

The results of the Phase 1a interim analysis will confirm the dosing regimens to be used in Phase 1b. Dose reductions (ramucirumab), delays, and discontinuations may occur per the guidelines in Section 6.6.

Patients will be added to include 7 separate expansion cohorts, with dosing schedules corresponding to those in DLT Phase 1a, as shown in [Figure JVDF.1](#). Gastric patients will be assigned to Cohort A, A2, or B (Section 6.2).

The final analysis of safety and preliminary efficacy will occur approximately 2 years after the first patient received first study treatment. Interim analyses will occur at a cohort level when the patients have completed approximately 24 weeks of study treatment. The Phase 1b data will provide additional safety, tolerability, pharmacokinetics (PK) and pharmacodynamics, and preliminary efficacy data for the combination.

4.1.3. Study Period and Continued Access Definitions

Terms used to describe the periods during the study are defined below and illustrated in [Figure JVDF.2](#).

- **Baseline/Screening:** begins when the informed consent form (ICF) is signed, and ends at the first study treatment (defined as receiving either ramucirumab or pembrolizumab); if no study treatment is given, baseline/screening ends at discontinuation. Lasts up to 28 days.
- **Study Period:** begins at the time of first study treatment and ends at study completion, which occurs approximately 2 years after the first patient received first study treatment (Section 4.4).
 - **Study Treatment Period:** begins with the day of the first patient's first study treatment and ends the day that the decision is made to discontinue study treatment (discontinuation of both study drugs; Section 7.1). Individual patients who enroll in Study JVDF may continue treatment for up to 35 cycles (approximately 2 years), until they have confirmed progressive disease or discontinued study treatment for any other reason.
 - **Postdiscontinuation Follow-Up** consists of the following 2 phases.
 - **Short-Term (Safety) Follow-Up:** begins the day after the patient and the investigator agree that the patient will discontinue study treatment and ends with the short-term follow up visit, to occur approximately 30 days thereafter.
 - **Long-Term (Survival) Follow-Up:** begins the day after short-term follow-up is completed and ends with the patient's death, loss to

follow-up, or overall study completion, whichever is earlier. The long-term follow-up visit will occur approximately 90 days after the decision is made to discontinue from study treatment. Subsequent follow-up (not a formal visit) will occur approximately every 90 days thereafter, for up to approximately 2 years from the first study treatment (Attachment 1).

- **Continued Access Period:** begins after study completion (final analysis and evaluation of the study endpoints) and ends at end of trial (defined in Section 4.4). In the continued access period, individual patients may continue the current study treatment after study completion, as long as they experience ongoing clinical benefit (details in Section 6.10). Sites will be notified when the continued access period is to begin and end.

Patients who are in short-term follow-up when the continued access period begins will complete the 30-day short-term follow-up visit and then discontinue the study.

Patients who are in long-term follow-up when the continued access period begins will be discontinued from long-term follow-up.

[figure not shown]

Figure JVDF.2.

Study period and continued access diagram.

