4.4. End of Study/Trial Definition

Study completion for Phase 1 of Study JVDF occurs after the clinical trial database is locked and the final analysis and evaluation of the study endpoints of dose-expansion Cohorts A through E has occurred based on data available approximately 2 years after the first patient received first study treatment. The end of trial occurs after study completion and when the last patient has discontinued study treatment and completed any applicable continued access follow -up (last patient last visit). Section 6.1 describes the maximum duration of study treatment.

5. Study Population

Prospective approval of protocol deviations to recruitment and enrollment criteria (also known as protocol waivers or exemptions) is not permitted.

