Serious adverse event collection begins after the patient has signed informed consent and has received IP and ends 90 days following cessation of treatment, or 30 days following cessation of treatment if the patient initiates new anticancer therapy, whichever is earlier. If a patient experiences an SAE after signing informed consent, but prior to receiving IPs, the event will not be reported as serious unless the investigator feels the event may have been caused by a protocol procedure.

Study site personnel must alert Lilly or its designee of any **serious** adverse event (SAE) within 24 hours of investigator awareness of the event via a Sponsor-approved method. If study site

personnel contact Lilly or its designee by telephone regarding an SAE, study site personnel must also immediately provide official notification on study-specific SAE forms.

This 24-hour notification requirement refers to the initial SAE information and all follow-up SAE information.

Planned surgeries should not be reported as SAEs unless the underlying medical condition has worsened during the course of the study.

Planned hospitalizations or procedures for preexisting conditions that are already recorded in the patient's medical history at the time of study enrollment should not be considered SAEs.

Serious adverse events due to disease progression, including death, should not be reported unless the investigator deems them to be possibly related to the IPs.

The investigator does not need to actively monitor patients for AEs once the trial has ended, unless provided otherwise in the protocol; however, if an investigator becomes aware of an SAE occurring after the patient's participation in the trial has ended, and the investigator believes that the SAE is related to a protocol procedure or IPs, the investigator should report the SAE to the Sponsor, and the SAE will be entered in the Lilly Safety System.

Information on SAEs expected in the study population independent of drug exposure and that will be assessed by the Sponsor in aggregate periodically during the course of the trial may be found in the pembrolizumab and ramucirumab IBs.

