5.2.1.3. Adverse Event-Related Variables

Adverse event-related variables are listed below:

- **Dose-limiting toxicity (DLT):** Please refer to Section 5.2.1.1 for the definition of DLT.
- **Adverse event (AE)** is defined as any untoward medical occurrence in a patient administered a pharmaceutical product, without regard to the possibility of a causal relationship.
- **Treatment-emergent adverse event (TEAE)** is defined as an event that first occurred or worsened in severity between first dose of study treatment and 90 days after the last dose of study treatment and related SAEs reported beyond 90 days after the last dose of study treatment, where last dose stands for actual dose, that is, 0 dose is not counted as last dose.
- **Adverse events of special interest (AESIs)** for ramucirumab include arterial thromboembolic events (ATEs)*, congestive heart failure (CHF)*, fistula (gastrointestinal [GI]* and non-GI), gastrointestinal perforation (non-fistula)*, hemorrhage (also GI hemorrhage as a subcategory and pulmonary hemorrhage [composite term])*, healing complication, hypertension*, infusion-related reaction (IRR) including anaphylactic reaction, liver injury/failure*, proteinuria*, reversible posterior leukoencephalopathy syndrome (RPLS), and venous thromboembolic events*.

Notes:

1. All AESIs are compound level.
2. Each AESI is defined by a set of MedDRA preferred terms (PTs).
 - 2.1. For RPLS, the PTs were directly selected from MedDRA.
 - 2.2. For AESIs marked with *, the PTs were selected from the applicable standardized MedDRA queries (SMQs) v.15.0 or higher.
 - 2.3. For non-GI fistula, all PTs containing the text string “fistula” need be used for analysis.
 - 2.4. For the rest of the AESIs, the PTs were identified through medical review of all unique PTs collected in all ramucirumab studies for compound-level AESIs.
3. Categories of AESIs may be modified as the understanding of the safety of the investigational drug increases. The final list of categories will be reported in the clinical study report (CSR).

- **Consolidated AEs** include abdominal pain, anemia, fatigue, hyperbilirubinaemia, hypercalcaemia, hyperkalaemia, hypermagnesaemia, hypernatraemia, hyperphosphataemia, hypoalbuminaemia, hypocalcaemia, hypokalaemia, hypomagnesaemia, hyponatraemia, hypophosphataemia, intestinal obstruction, leukopenia, myocardial infarction, neuropathy, neutropenia, rash, renal failure, thrombocytopenia, and urticarial.

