5.3.8. Deaths, Serious Adverse Events, and Other Significant Adverse Events

Reasons for deaths will be summarized separately for 1) all deaths, 2) deaths up to 30 days after the last infusion of study treatment, and 3) deaths after 30 days of last infusion of study drug. Reasons of deaths will also be listed.

Serious adverse events (SAEs) will be summarized by PT and repeated for events deemed by the investigator to be possibly related to study medication, with consolidated summary performed if needed. SAEs will be summarized both up to 30 and 90 days after end of therapy. A listing of SAEs will be produced.

In addition, the following analyses will be performed:

- AESIs for ramucirumab by PT
- AESIs for ramucirumab by PT related to study drug
- ECIs for pembrolizumab by PT
- ECIs for pembrolizumab by PT related to study drug
- Listing of AESIs, sorted in the order of phase, cohort, AESI category, PT, and patient identification
- Listing of AEs with outcome of death or discontinuation

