5.3.15. Interim Analysis

For the Phase 1a part of the study, the available safety and PK data will be reviewed on a cohort-by-cohort basis. The purpose of these data reviews is to evaluate the safety and tolerability for each dose schedule and determine if a DLT has been observed. The investigators and the Lilly study team will evaluate the totality of data to determine whether or not to move into the Expansion Phase 1b.

For the Phase 1b part of the study, in Cohorts A, B, C, or D, the final analysis of safety and preliminary efficacy will occur approximately 2 years after the first patient (from any of the above cohorts) received first study treatment. For Cohorts A1, A2, or E, the final analysis of

safety and preliminary efficacy will occur approximately 2 years after the first patient (from any of the above cohorts) received first study treatment. Interim analyses will occur at a cohort level when the patients have completed approximately 24 weeks of study treatment or discontinued for any reason. The interim analyses may be combined if they are expected to occur within approximately 1 month, and interim analyses may also be combined with the ongoing trial-level safety review or annual safety review for annual safety update reporting. The study is considered complete when analyses for all cohorts are conducted and no further analyses will be performed (including biomarker analyses).

An independent data monitoring committee may be initiated if 1 or more additional cohorts will be expanded to further explore safety and efficacy for the ramucirumab and pembrolizumab combination.

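### Protocol 4.1.3 releases off-treatment patients before the required 90-day SAE and ECI window closes, and the 90-day SAE summary does not show how many windows are unfinished at the data cut

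*Protocol*

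**What the plan says.** **Collection window.** Protocol 8.2.1.2 has SAE collection start with study drug, and it "ends 90 days following cessation of treatment, or 30 days following cessation of treatment if the patient initiates new anticancer therapy, whichever is earlier". Table JVDF.7 asks for all SAEs through the 90-day visit. Section 8.2.1.1.3 takes ECIs to 90 days after discontinuation, or to 30 days after new anticancer therapy begins, if earlier.

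**Release.** Section 4.1.3 acts when continued access begins, which is after study completion. For short-term follow-up: "Patients who are in short-term follow-up when the continued access period begins will complete the 30-day short-term follow-up visit and then discontinue the study". For long-term follow-up: "Patients who are in long-term follow-up when the continued access period begins will be discontinued from long-term follow-up". Patients who carry on in continued access have a follow-up of about 30 days (Section 6.10 and Attachment 1).

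**Analysis.** Protocol 4.4 describes one completion for Cohorts A through E, "based on data available approximately 2 years after the first patient received first study treatment". SAP 5.3.15 instead gives Cohorts A to D and Cohorts A1, A2 and E separate 2-year clocks, and adds: "The study is considered complete when analyses for all cohorts are conducted and no further analyses will be performed (including biomarker analyses"). SAP 5.2.1.3 counts an event as a TEAE if it arises or worsens "between first dose of study treatment and 90 days after the last dose of study treatment", plus related SAEs reported later. SAP 5.3.8 states: "SAEs will be summarized both up to 30 and 90 days after end of therapy". The safety set is all treated patients (SAP 5.2.1.7), proportions are n/N (SAP 5.3.1), and missing data are not imputed (SAP 5.2.1.6).

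**The concern.** Safety is the primary objective, and Protocol 6.6.2 itself warns that pembrolizumab events can appear months after the last dose. The 90-day window exists to catch them. Two separate things go wrong.

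First, the collection rules contradict each other. A site with a patient 45 days off treatment when continued access begins is told by 4.1.3 to end follow-up, and by 8.2.1.2 and Table JVDF.7 to keep collecting SAEs to day 90. After release, only related SAEs that the investigator happens to learn of are reported. They go to the sponsor's safety system and not to the collection database (Table JVDF.7).

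Second, the data cut is fixed by calendar, while treatment may itself last about 2 years. Patients whose 90-day window is open, or has not yet started, sit in the denominator of the 90-day SAE summary beside patients observed in full. Events that fall after the cut are not counted, so the proportion can understate late SAEs, and a reader cannot tell how many patients are affected.

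**Working it through.** **The plan's own figure.** 35 cycles x 21 days = 735 days, and 735 / 365.25 = 2.01 years. This agrees with the stated maximum of approximately 2 years (Protocol 6.1, 6.1.1).

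**Window against cut, first patient, no delays.**
- Last dose, Schedule 2: 34 x 21 + 1 = Day 715. Schedule 1 (Day 8): 34 x 21 + 8 = Day 722.
- 90-day window ends: 715 + 90 = Day 805; 722 + 90 = Day 812.
- Cut at about Day 730: short by 805 - 730 = 75 days, or 812 - 730 = 82 days.
- Any last dose after trial day 730 - 90 = 640 leaves an unfinished window. Later enrolment or dose delays make it more likely.

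The same arithmetic applies to Cohorts A1, A2 and E on their own clock in SAP 5.3.15.

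**Release against window, patient by patient.**

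| Status when continued access begins | 4.1.3 / 6.10 | 8.2.1.2 and 8.2.1.1.3 | Collection lost |
|---|---|---|---|
| Off treatment, before the 30-day visit | leaves after that visit | to day 90 | about days 31-90 |
| Off treatment, days 31-89 | leaves at once | to day 90 | remainder to day 90 |
| Off treatment, day 90 or later | leaves at once | window closed | none required |
| Continues in continued access | about 30 days after stopping | to day 90 | about days 31-90 |

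If new anticancer therapy has started, the SAE window shrinks to 30 days and the SAE conflict disappears. In the last row, Table JVDF.7 has its own 30-day line for continued access, so the conflict there is with the text of 8.2.1.2 and 8.2.1.1.3.

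**Size, on assumptions only.** The documents give no accrual rate or expected time on treatment. I assumed uniform accrual, exponential time to last dose capped at 34 x 21 = 714 days, a single cut at Day 730, no removal for death and no new-therapy exception. Selected results, as % of patients:

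| Accrual (months) | Median treatment (months) | On treatment at cut | Off, <30 days | Off, 30-90 days | Any unfinished window |
|---|---|---|---|---|---|
| 6 | 2 | 0.1 | 0.0 | 0.1 | 0.2 |
| 6 | 8 | 15.3 | 2.6 | 3.3 | 21.2 |
| 12 | 4 | 5.2 | 1.0 | 2.5 | 8.8 |
| 18 | 2 | 2.0 | 0.8 | 2.8 | 5.5 |
| 18 | 8 | 29.8 | 3.0 | 6.1 | 38.9 |

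(Rows may not add exactly because of rounding.)

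A second model floored treatment to 21-day cycles and added survival after the last dose with a median of 150 days. It used accrual over months 0-9, 0-18 or 6-18, and median treatment of 2.1 to 8 months. Patients alive, off treatment and 30-89 days from last dose were 0.2% to 5.6%; all those alive, off treatment and under 90 days were 0.2% to 6.4%. Large totals came from patients still on treatment: with accrual over months 0-18 and median treatment of 8 months, 31.1 of 36.3 percentage points.

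**The case against.** - **The release cannot alter the final tables.** A reader might infer that 4.1.3 biases the final safety analysis. It does not: continued access starts after lock and final analysis, so only the data cut shapes those tables. The release causes a separate loss of collection. This objection stands.
- **Full treatment does not rule out 90 days of observation.** A reader might infer that nobody given 35 cycles can be followed that far. Follow-up runs on between cut and release, and the 2-year point is approximate. What fails is inclusion in that data cut.
- **The late cohorts are not bound to the first patient's clock.** Under a single cutoff, accrual over months 6-18 gives totals up to about 45%. SAP 5.3.15 gives A1, A2 and E their own clock, and completion waits for all cohorts, so A to D may stay in follow-up past their own final analysis. The high figures do not hold under the SAP. No analysis of the extra A to D data is specified, however, and Protocol 4.4 still describes one completion.
- **Later analysis is not forbidden.** The closing sentence of SAP 5.3.15 can be read as defining completion. SAP 5.3.1 allows exploratory analyses, and SAEs in continued access still enter the database. What is missing is a pre-specified rerun.
- **The 90-day limit is a counting rule.** SAP 5.3.8 says which events count and does not claim that every patient was observed for 90 days. A 30-day summary sits beside it, and DLTs are unaffected. That is fair, but it is a reason to print how many windows are incomplete.

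**Conclusion.** The point holds in two limited parts. Section 4.1.3, and the 30-day follow-up after continued access, contradict the 90-day SAE and ECI rules for patients who have not reached 90 days and have no earlier end point. Separately, the calendar cut leaves some 90-day windows unfinished, and the SAP neither counts those patients nor says how the 90-day summary treats them.

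The first-patient gap of 75 to 82 days follows from the documents' own figures, taking 2 years as Day 730. The share of patients affected does not. Under the assumed accrual and treatment times, about 0.2% to 6% are alive, off treatment and 30 to 89 days from last dose at the cut. Those under 30 days add to this, because they leave after the 30-day visit. The count at release may differ from the count at the cut, and starts of new anticancer therapy would lower it. The larger totals mainly describe patients whose post-treatment window has not opened. The effect on the 90-day SAE proportion is an undercount of unknown size.

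**What to change.** 1. **Protocol 4.1.3, with 6.10 and Attachment 1.** Reconcile with 8.2.1.1.3, 8.2.1.2 and Table JVDF.7, so that patients off treatment when continued access begins stay for SAE and ECI collection until the already planned 90-day contact, or the earlier end point those sections allow. State which window applies after continued access.
2. **SAP 5.3.8.** Keep the all-treated 90-day SAE table. Print beside it the number still on treatment and the number under 90 days from last dose at the cut. Add a supportive table limited to patients whose last dose was at least 90 days before the cut, whatever their vital status. Do not add back patients who died inside an unfinished window while dropping comparable survivors, because inclusion would then depend on outcome. With the assumed 150-day median, true 90-day mortality is 1 - 2^(-90/150) = 34%; that selection raised it to as much as 36.4%. The restricted table also omits the longest-treated patients, so it should stay supportive.
3. **SAP 5.3.15.** Pre-specify one rerun of the SAE, TEAE and death tables at end of trial, using the continued-access data already being collected. Reconcile the definition of study completion with Protocol 4.4.

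Cost: a short delay before a few patients leave the study, some text in each document, one extra table and one rerun of existing programs. No added patients or new procedures.

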4.2. Rationale for Study Design

The general rationale for the study design is described in the Introduction (Section 2). The details regarding dose selections are described below.

4.2.1. Dose Selection for Ramucirumab

4.2.1.1. Rationale for Selection of Ramucirumab Dose Schedule 1 (8mg/kg every 3 weeks on Day 1 and Day 8 in Patients with Gastric-GEJ Cancer and BTC)

Ramucirumab Dose Schedule 1 (8 mg/kg on Days 1 and 8; 21-day cycle) was based on exposure-response analyses in REGARD (8 mg/kg every 2 weeks [Q2W]) and RAINBOW (8 mg/kg on Days 1 and 15; 28-day cycle).

Efficacy

Exposure-efficacy response analyses performed on data obtained from REGARD and RAINBOW demonstrated that an increase in exposure is associated with improved efficacy in terms of both overall survival (OS) and progression-free survival (PFS). In both studies, patients with greater-than-median ramucirumab exposure demonstrated significantly longer OS and PFS (smaller hazard ratio [HR]) as compared to patients with less-than-median ramucirumab exposure.

These findings were consistent for all 4 exposure measures tested: minimum concentration after first dose administration ($C_{\min,1}$), minimum concentration at steady state ($C_{\min,ss}$), maximum concentration at steady state ($C_{\max,ss}$), and average concentration at steady state ($C_{ave,ss}$).

Safety

[figure not shown]
Weekly doses of ramucirumab ranging from 2 to 16 mg/kg were evaluated in the Phase 1 Study JVBM. A maximum tolerated dose (MTD) for weekly dosing was identified as 13 mg/kg. Every-2-week (6 to 10 mg/kg) and every-3-week (15 to 20 mg/kg) dose regimens were evaluated in another dose-ranging Study JVBN. All dose regimens in Study JVBN were well tolerated and no MTD was identified in this study.

REGARD demonstrated a well-tolerated safety profile in the gastric-GEJ cancer monotherapy setting. Due to the low incidence of hypertension and neutropenia, no safety-exposure relationship was identified for these treatment-emergent adverse events.

In RAINBOW, the overall safety profile was also considered manageable, although increasing ramucirumab exposure was correlated with increased incidence of Grade 3 or greater hypertension, neutropenia, and leukopenia. There were no Grade 4 or 5 hypertension events. Hypertension was managed primarily by the use of standard antihypertensive medication, and the association of neutropenia with ramucirumab exposure did not appear to translate to an increased risk of febrile neutropenia with higher ramucirumab exposure.

These data indicate that there may be an opportunity to further improve ramucirumab activity in the gastric-GEJ indication. Based on PK simulation, Dose Schedule 1 (8 mg/kg on Days 1 and

8; 21-day cycle) may produce $C_{min,ss}$ greater than the median $C_{min,ss}$ obtained from the standard 8-mg/kg Q2W regimen in at least 70% of the patient population (Figure JVDF.3) and therefore may produce better clinical efficacy outcomes relative to the 8-mg/kg Q2W regimen. The ramucirumab-related safety risk in the gastric-GEJ cancer indication may not be significantly increased using Dose Schedule 1, as this dose is approximately 60% lower than the maximum tolerated weekly dose identified in the Phase 1 dose-escalation Study JVBM (13 mg/kg weekly). Thus, Dose Schedule 1 may further enhance the efficacy in Gastric-GEJ indication, and may be the appropriate dosing regimen for BTC as well.

Abbreviations: $C_{min,ss}$ = minimum concentration at steady state; Q = every; W = week. Box plots depict the 5th, 25th, 50th, 75th, and 95th percentiles calculated from 1000 simulation iterations.

Figure JVDF.3.

Predicted $C_{min,ss}$ following different dose regimens.

